#### 4.2.9. Date of last assessment

Date of last assessment will be the date of the last visit per subject as recorded on the subject visit date CRF (SV (Study Visits) SDTM dataset).

#### 4.2.10. Planned and actual treatment

Planned treatment will be the one assigned per the randomization list. Possible treatment groups are:

- Placebo
- NT-814 40 mg once a day

- NT-814 80 mg once a day
- NT-814 120 mg once a day
- NT-814 160 mg once a day

Actual (received) treatment might be different if the kit(s) actually dispensed does not correspond to the kit(s) allocated by IWRS. Thus, actual treatment groups will be derived – for patients belonging to the Safety Analysis Set – according to the majority of treatment dispensed to the patient. Indeed, kits are dispensed at Baseline, Week 4 and Week 8 visits. In case of there is no treatment given in majority, then the actual treatment group will correspond to the kit actually dispensed to the subject at Visit 3 for the first treatment period from baseline to Week 4. If the information on the kit number is not available at the time of the analysis, the actual treatment will be considered as equal to the planned one.

In practice, this means that a dispensing error could result in a subject being analysed in an actual treatment group different from its planned treatment group in case of dispensing error.

Any occurrence of incorrectly administered treatment should be recorded as a PD, and will be reviewed at the BDRM to assess on an individual case by case basis which treatment group the subject will be allocated to.

#### 4.2.11. Baseline definition

Baseline is defined as the data most recently collected prior to the first randomised treatment intake date/time. If time of the corresponding data (e.g. Questionnaires) is not collected then, we will assume that the assessment at Visit 3 is performed as planned, i.e. prior to the treatment intake.

The baseline assessment for hot flushes will be calculated using the last 7 days (not necessarily consecutive days) with an available data in the evening and/or the morning of the baseline diary completion period. A diary day is comprised of the evening entry of this day and the morning entry of the following day, in that order.

Mean daily frequency = Sum of number of hot flushes filled in the diary during the last 7 diary days (with at least one available data in the evening and/or morning) divided by 7.

Mean weekly severity = (number of moderate hot flushes for 7 days) x 2 + (number of severe hot flushes for 7 days) x 3] / (total number of moderate to severe hot flushes over 7 days).

Mean daily HF score = Sum of (frequency x severity) filled in the diary during the last 7 days (with at least one available data in the evening and/or morning) divided by 7. Severity is graded by the women from 1 to 3 (1 = mild; 2 = moderate; 3 = severe).

For the primary efficacy endpoint analyses and several of the secondary endpoint analyses, only moderate and severe HF data are included in the calculations. For these analyses the mild data recorded in the diary will be excluded from the baseline values.

A diary day comprises an evening entry and a morning entry, in that order. If a diary has been completed on a particular day but is missing data on HF that day, then it will be assumed that there was no HF on that day. This diary will not be used for the 7 days of baseline data. Only diary with available data will be used in baseline derivation.

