#### **7.2 Inclusion Criteria**

Subjects must meet all the inclusion criteria listed below.

1. Females aged 40 to 65 years, inclusive, at Screening Visit 1.
2. Able to understand and comply with the requirements of the study and give informed consent.
3. Postmenopausal, defined as: (i) at least 12 months of spontaneous amenorrhea, or (ii) at least 6 months of spontaneous amenorrhea with serum FSH levels > 40 mIU/ml and a serum oestradiol concentration of < 30 pg/mL, or (iii) at least 6 weeks postsurgical bilateral oophorectomy with or without hysterectomy.
4. Body mass index between 18 and 38 kg/m^2, inclusive, at Screening Visit 2.
5. Negative urinary pregnancy test at Screening Visit 2.
6. In good general health, in the opinion of the investigator, based on the medical history, physical examination, 12-lead ECG, vital signs and clinical laboratory tests assessed at Screening Visit 2.
7. Subject has completed the paper diary for at least 6 days between Screening Visits 1 and 2 and has recorded an average of at least 8 moderate or severe hot flushes per day (including night-time) over the last 5 days that the paper diary was completed (assessed at Screening Visit 2).

---

 Durations are relative to screening visit 1

 Subjects who do not clearly fall into 1 of the 3 defined categories, but who are hormonally post-menopausal (serum FSH levels > 40 mIU/ml and a serum oestradiol concentration of < 30 pg/mL) and of an appropriate age, may also be considered for inclusion.

8. Subject has completed the electronic diary for at least 9 days between Screening Visit 2 and Day 1 and has recorded an average of at least 7 moderate or severe hot flushes per day (including night-time) over the last 7 days that the eDiary was completed (assessed at the Baseline Visit).

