### 3. SUBJECT POPULATIONS

#### 3.1. Population Definitions

The following subject populations will be evaluated and used for presentation and analysis of the data:

**Screen Analysis Set:** the screened population will include all subjects with informed consent.

**Randomized Analysis Set:** the randomized population will include all subjects with a randomization date and number.

**Safety Analysis Set:** All subjects who receive at least one dose of double-blind study drug irrespective of treatment received. Subjects will be analysed according to treatment received.

**Full Analysis Set (FAS):** All randomised subjects who received at least one dose of double-blind study drug, irrespective of treatment received, and have hot flush data for at least 7 days' worth of post-treatment assessments (i.e. requirement for the primary efficacy endpoint). Subjects will be analysed according to randomised treatment. This is the primary efficacy analysis set for the study.

**Modified Full Analysis Set (mFAS):** All subjects in the FAS excluding those who took non-hormonal treatments (anti-depressants, alpha-2 agonists, gabapentinoids and cannabis) or over the counter herbal treatments (intended to treat menopausal symptoms) that may have had a confounding effect on hot flash frequency and/or severity at any time during the study (defined as within 28 days before the start of Screening Visit 2 through to the Week 12 visit, inclusive). The medications entered in EDC have been reviewed by Sponsor's blinded Medical Expert, and the following final list of PREFERRED NAME was confirmed:

CLONIDINE  
CLONIDINE HYDROCHLORIDE  
CIMICIFUGA RACEMOSA  
TRIFOLIUM PRATENSE  
CIMICIFUGA RACEMOSA;HYPERICUM PERFORATUM  
CANNABIS SATIVA  
GABAPENTIN  
PREGABALIN  
AMITRIPTYLINE  
NORTRIPTYLINE  
CITALOPRAM  
CITALOPRAM HYDROBROMIDE  
ESCITALOPRAM  
ESCITALOPRAM OXALATE  
FLUOXETINE  
FLUOXETINE HYDROCHLORIDE  
PAROXETINE  
PAROXETINE HYDROCHLORIDE  
SERTRALINE  
SERTRALINE HYDROCHLORIDE  
BUPROPION  
BUPROPION HYDROCHLORIDE  
DESVENLAFAXINE  
DESVENLAFAXINE SUCCINATE

DULOXETINE  
DULOXETINE HYDROCHLORIDE  
VENLAXAFINE  
VENLAFAXINE HYDROCHLORIDE  
MIRTAZAPINE  
TRAZODONE  
TRAZODONE HYDROCHLORIDE  
VORTIOXETINE HYDROBROMIDE  
CALCIUM;CIMICIFUGA RACEMOSA EXTRACT;GENISTEIN;HERBAL EXTRACT  
NOS;MAGNESIUM;PIPER METHYSTICUM RHIZOME

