### 3.2. Protocol Deviations

Protocol deviations are defined as a deviation from the approved protocol.

Prior to database lock, NeRRe will be responsible for producing the final protocol violation file (formatted as a Microsoft Excel file), in collaboration with the data monitoring group; this file will include a description of the protocol violation and the categorization as minor/major, relevant / not relevant. Deviations classified as relevant will result in exclusion of the subject from the Per Protocol Population. This file will be finalized and signed prior to hard database lock, after the blinded data review meeting (BDRM).

In addition, the following protocol deviations will be programmatically derived by Cytel:

- 1) Category = Non-compliance with diary completion
  - PD Reference 3.9: Less than 70% compliance with hot flush diary completion at Baseline (Visit 3).
  - PD Reference 3.10: Less than 70% compliance with hot flush diary completion at Week 4 (Visit 5).
  - PD Reference 3.11: Less than 70% compliance with hot flush diary completion at Week 12 (Visit 7).
  - PD Reference 3.12: Less than 70% compliance with hot flush diary completion at Week 2 (Visit 4), Week 8 (Visit 6) or Week 16 (Visit 8).

Compliance will be calculated for Baseline, Week 2, Week 4, Week 8, Week 12 and Week 16, using the same 7 days (or less than 7 days if this is the case per the rules defined in section 4.3.2) used in the analysis of HF frequency & severity.

The 70% cut-off essentially means that at least 10 of the 14 possible diary entries will need to have been completed for the subject to be in the PP population.

2) Category = Non-compliance with study medication

PD Reference 4.2: Subject <80% compliant with once-daily dosing of IMP.

IMP compliance will be based on the number of capsules taken (section 4.8.1). The compliance calculation should be across the whole 12-week double-blind treatment period (not visit specific). IMP should not be missing.

Relevant protocol deviations will be summarised by treatment group for the Randomised Analysis Set. All protocol violations will be presented in the data listings.

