#### 4.2.7. Missing, Unused, and Spurious Data

In general, there will be no substitutions made to accommodate missing data points. All data recorded on the CRF will be included in data listings that will accompany the clinical study report.

Sensitivity analyses may be performed, and are detailed in the corresponding efficacy endpoint sections.

Clinical laboratory values as “<X” where X is the numerical value of the limit of quantification (LOQ) established by the laboratory will be imputed by LOQ/2 for summaries in the tables.

Clinical laboratory values as “>X” where X is the numerical value of the limit of quantification (LOQ) established by the laboratory will be imputed by LOQ for summaries in the tables.

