#### 4.3.2. Efficacy analysis

At each interim review, summaries by dose group will be provided on the FAS for each of the following:

- Mean daily frequency of moderate and severe HF at baseline, mean daily frequency of moderate and severe HF at each study week, including Week 4 and mean change and percent change from baseline in the mean daily frequency of moderate and severe HF at each study week.
- Mean severity of moderate and severe HF at baseline, mean severity of moderate and severe HF at each study week, including Week 4, and mean change from baseline in the severity of moderate and severe HF at each study week.

If available, summaries of the same data at later time-points (Week 8 and Week 12) will also be reviewed.

Mean daily frequency at each study visit will be calculated using the same method as the one described in section 4.2.11 based on the last 7 days with at least one available data in the evening and/or morning before the corresponding visit.

Mean weekly severity at each study visit will be calculated using the following:

$$\frac{[(\text{number of mild hot flushes for 7 days}) \times 1 + (\text{number of moderate hot flushes for 7 days}) \times 2 + (\text{number of severe hot flushes for 7 days}) \times 3]}{\text{total number of mild, moderate and severe hot flushes over 7 days}}$$

If the number of hot flushes is equal to 0, then the mean severity will be set to 0.

These 7 last days with available data should be within the 14 days prior to the CRF study visit, so in the following window: [CRF Visit date – 14; CRF Visit date], with at least one day within

the last 7 days prior to the study visit. In case of withdrawal, the day this ET visit happened will be checked to see in which windows it is and then to assign the corresponding timepoint. If a CRF visit has already been done at that timepoint, then the CRF visit date will be used. If less than 7 days fulfil these rules, only the correct data will be used in the derivation, and formula will be adjusted using the right number of days as denominator. Morning diary data on the day of a Visit will be included in the derivation as the morning diary is actually associated with the previous calendar day (a complete day is an evening then a morning diary).

In addition, emerging data will be evaluated via the two adaptive following algorithms to evaluate the emerging data at Week 4:

- (i) a Bayesian adaptive Emax (S-shaped) dose-response model fit, and

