- (ii) a model based on isotonic regression (T-stat)

The models have been developed using the following prior assumptions:

1) On frequency of hot flushes:

- The mean reduction in the mean daily number of moderate and severe HF's in the placebo group is 4 per day
- Two target levels of test treatment: mean reduction from baseline in the mean daily number of moderate and severe HF's of 6 and 8
- Common standard deviation (SD) of 4.4
- Stopping guidelines for Emax if (a) the probability is > 90% that the mean hot flush reduction is at least 8 at that dose, or (b) the probability is <20% that the mean hot flush reduction is at least 5 (i.e., >80% probability that the mean hot flush reduction is <5).

2) On severity of hot flushes:

- The mean reduction in the severity of moderate and severe HF's in the placebo group is 0.44 per day
- Two target levels of test treatment: mean reduction from baseline in the severity of moderate and severe HF's of 0.66 and 0.88
- Common standard deviation (SD) of 0.55
- Stopping guidelines for Emax if (a) the probability is > 90% that the mean severity hot flush reduction is at least 0.88 at that dose, or (b) the probability is <20% that the mean severity hot flush reduction is at least 0.22 (i.e., >80% probability that the mean hot flush reduction is <0.22).

Emerging data (mean change from baseline in the frequency/severity of moderate and severe HF at Week 4) will be entered in COMPASS software using the Execute module. The following steps will be followed:

- Raw data from eDiaries will be provided to the Cytel blinded team by ERT, the CRF data will be provided by the Pharm Olam Data Management team
- Efficacy endpoints to be presented (see above) will be generated by the Cytel blinded team using the derivation described in this SAP
- Statistical descriptive tables for these endpoints will be produced by the Cytel blinded team using a dummy randomisation list

- Programs will be rerun by the Cytel unblinded team using the real randomisation list provided to the Cytel unblinded statistician
- Endpoint data for each patient along with their treatment arm will be entered into COMPASS.

Prior distributions, defined above and used for the simulation, will also be entered in the software. COMPASS has been developed as a software package for design of adaptive early stage trials within Cytel's suite of software programs for design, analysis, and implementation of clinical trials.

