#### 4.6.1. Co-primary analysis

The co-primary endpoints are the change from baseline in the mean daily frequency and mean weekly severity of moderate and severe hot flushes at Weeks 4 and 12.

For each timepoint (Baseline, Week 1, Week 2, Week 4, Week 8, Week 12) summaries will be produced which use data from the 7 days with at least one available eDiary data entry in the evening and/or the morning before the Visit date:

- These 7 days do not need to be consecutive.
- As the data entered in the morning diary is assigned to the previous calendar day (a diary day comprises an evening and a morning entry, in that order) the morning diary with the same calendar date as the Visit day may be included in the calculation.
- For Week 1, the first 7 post-baseline days with at least one available data in the evening and/or the morning will be used.

The methods for calculating the endpoint are the same as described in section 4.2.11.

Absolute and changes from baseline in the mean daily frequencies and mean weekly severity of moderate and severe hot flushes will be summarised by treatment group. Percent changes from baseline in the mean daily frequencies will be also summarised.

The change from baseline will be calculated as follow:

Mean daily frequency (or mean severity) at week 4 (or Week 12) – Mean daily frequency (or mean severity) at baseline.

The percent change from baseline will be calculated as follow:

(Change from baseline / Mean daily frequency at baseline) \* 100.

The mean change from baseline and the corresponding 95% confidence interval (CI) will be displayed graphically by visit on the observed values and by treatment groups.

Bar graphs of the change from baseline at Week 4 and Week 12 will be produced for each treatment group.

The change from baseline endpoint will be analysed using a Mixed-Effect Model Repeated Measures (MMRM) incorporating post-randomization data collected up to treatment discontinuation at weeks 12 (Week 1, 2, 4, 8 and 12 will be included; Week 16 visit data will not be included in the model) and with consideration of the variance-covariance matrix of the repeated measures.

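### A diary day with one of its two entries missing counts as a full day, so mean daily hot flush frequency is undercounted in the FAS

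*SAP*

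**What the plan says.** - **The rule.** SAP 4.2.11 pairs an evening entry with the following morning's entry. Mean daily frequency is the sum of flushes recorded "during the last 7 diary days (with at least one available data in the evening and/or morning) divided by 7".
- **Visits.** SAP 4.6.1 uses "data from the 7 days with at least one available eDiary data entry in the evening and/or the morning before the Visit date" and refers back to 4.2.11 for the calculation.
- **Denominator.** If fewer than seven days qualify, SAP 4.3.2 says the "formula will be adjusted using the right number of days as denominator". It counts days, not entries.
- **Imputation.** SAP 4.2.7: "In general, there will be no substitutions made to accommodate missing data points".
- **Completeness.** FAS subjects must "have hot flush data for at least 7 days' worth of post-treatment assessments" (SAP 3.1), with no minimum number of entries. The only entry-level limit is in SAP 3.2, where "at least 10 of the 14 possible diary entries will need to have been completed for the subject to be in the PP population".
- **True zeros.** The eDiary in Protocol Appendix C has its own field for no flushes, once for the day and once for the night. Appendix C warns that the version used may differ slightly.
- **Contrast.** For night-time awakenings, SAP 4.6.2.1 counts a day only if the morning entry is there.
- **A separate conflict.** For a completed diary with flush data missing, SAP 4.2.11 first assumes there were no flushes and then says that diary is not used.

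**The concern.** An absent entry is missing data, and the diary form gives a subject a way to record a true zero. The rule still treats the absent half as zero, because the day stays whole in the denominator. The affected quantities are the two frequency co-primaries, the hot flush score, the responder endpoint and the frequency inputs to the interims. Mean severity is a ratio and is not pulled to zero in this way.

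Within a subject, gaps after baseline overstate improvement and gaps at baseline understate it. Between arms, equal gaps shrink the estimated difference, and unequal gaps create a false one in favour of the arm that misses more entries. The interim algorithms use absolute targets, a "mean reduction from baseline in the mean daily number of moderate and severe HF's of 6 and 8", so an error in level matters there even when the arms are balanced. The MMRM cannot correct any of this, because the visit value is present and looks observed. The ANCOVA and Wilcoxon analyses use the same derived value.

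**Working it through.** **The plan's own figures.** For a difference of 8 - 4 = 4, SD 4.4, two-sided 0.05 and 95% power (SAP 4.1), the noncentral t gives 33 per group (power 95.3%), as stated. At 30 per group, power is 93.3%. The 70% diary limit is 0.70 x 14 = 9.8, so 10 entries (10/14 = 71.4%; 9/14 = 64.3%), also as stated.

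**One subject.** Assume a true 10 per day, 6 by day and 4 by night. With j of 7 mornings missing the rule gives (7 x 6 + (7 - j) x 4)/7: 8.86 for j = 2, 7.71 for j = 4, and 6.00 for j = 7. Adding separate evening and morning means gives 10.0 each time.

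**Random gaps.** If each entry is missing independently at rate m, a day is kept with probability 1 - m². The share of entries present on kept days is (1 - m)/(1 - m²) = 1/(1 + m), so the undercount is m/(1 + m), whatever the day/night split.

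| m | Undercount | True difference of 4.0 reads as |
|---|---|---|
| 5% | 4.8% | 4/1.05 = 3.81 |
| 10% | 9.1% | 4/1.10 = 3.64 |
| 15% | 13.0% | 4/1.15 = 3.48 |

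**Unequal gaps, true 6 per day in both arms.** 10% against 5%: 6/1.05 - 6/1.10 = 0.26 per day. 15% against 5%: 6/1.05 - 6/1.15 = 0.50 per day.

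**Clustered gaps.** With k one-entry days of seven and a share s of flushes in the missed half, frequency is multiplied by f = 1 - ks/7. For s = 0.3, 0.5 and 0.7:

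- k = 3: f = 0.871, 0.786, 0.700. A true 40% reduction with these gaps after baseline only reads as 1 - 0.6f = 47.7%, 52.9%, 58.0%.
- k = 4, the most the PP limit allows: f = 0.829, 0.714, 0.600, an undercount of 17%, 29% or 40%.
- Eligibility (Protocol 7.2) needs a subject who "has recorded an average of at least 7 moderate or severe hot flushes per day". With k = 4 at baseline the true mean must be at least 7/f = 8.4, 9.8 or 11.7, if the eDiary vendor counts the same way. Protocol 8.6.5 does not say.

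**Responders and interim targets, 10% random gaps.** After baseline only, a true 45% reduction reads as 1 - 0.55/1.1 = 50%, and a true 78% as 1 - 0.22/1.1 = 80%. With equal gaps at baseline and after, percent change is unaffected. From a baseline of 11 (Protocol Appendix B cites about 10 to 12), a true reduction of 5.5 reads as 11 - 5.5/1.1 = 6.0 with gaps after baseline only, and as 5.5/1.1 = 5.0 with gaps at both.

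**Power.** Equal gaps scale the difference and the SD together: 3.64 with SD 4.0 gives 93.3% at 30 per group, the same as 4.0 with SD 4.4. A simulation checked this, with 4,000 trials and 30 per arm. Assumptions: true baseline gamma, mean 11, SD 3.5, with the entry criteria applied; subject means after baseline gamma, SD 4.0, arm means 6 and 2; Poisson counts split 60/40; last 7 kept days of 14; ANCOVA on baseline.

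| Missing entries, current rule | Estimate | Power | Residual SD |
|---|---|---|---|
| None | 3.97 | 92.1% | 4.02 |
| 10% after baseline only | 3.61 | 91.5% | 3.71 |
| 10% at baseline and after | 3.64 | 91.5% | 3.69 |
| 15% at baseline and after | 3.46 | 92.2% | 3.56 |

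Separate means with 10% missing at both gave 4.01 and 92.3%.

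With a true 6 per day in both arms and 5% missing at baseline, 10% against 5% gave a false 0.26 and 5.7% rejection. 15% against 5% gave 0.46 and 7.4%. Rejection with no gaps was 4.4%. A repeat simulation gave 0.25 with 5.7% and 0.51 with 8.3%, and separate means brought rejection to 4.9%.

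**The case against.** The strongest reply accepts the mechanism and disputes its consequence. Only the level is always biased downward. The endpoint is change from baseline compared between arms, and that can move either way. Equal gaps are conservative and cost no power. A false difference needs gaps that differ by arm, and nothing in this double-blind trial points to that. At 10% against 5% it is 0.26 against a design effect of 4, and 5.7% rejection is only about two Monte Carlo standard errors (0.34 points) above 5%. The plan also has safeguards: diary compliance reviewed at visits, programmed deviations below 70%, a summary of relevant deviations by treatment group, a PP repeat of the co-primaries and a full eDiary listing. Finally, separate means assume that missing entries resemble recorded ones. If subjects skip entries on quiet nights, that rule overcounts.

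Much of this stands. The size is unknown, the direction in the contrast is not established, and the three- and four-day examples describe single subjects, not the trial. But none of the safeguards changes the primary FAS estimate. The deviation summary shows only subjects with 9 or fewer of 14 entries, so four one-entry days pass unseen, in the PP set too. The assumption behind the alternative is milder than the present one, which sets every missing half to zero.

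**Conclusion.** The concern holds. As written, the rule undercounts mean daily frequency in the FAS whenever a kept day lacks one entry that would have held flushes, and no planned FAS analysis tests this. At an assumed 10% of entries missing at random, the undercount is 9.1%. Equal gaps then turn a difference of 4.0 into 3.64 at unchanged power, and 10% against 5% adds a false 0.26 per day. The effect on change, responder status and the interim targets can go either way, depending on when and in which arm entries are missed. The mechanism follows from the SAP text. The sizes rest on assumed missing rates and day/night shares that the documents do not give. It should be fixed, since a derivation rule for two co-primary endpoints is wrong and cheap to put right.

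**What to change.** - Define mean daily frequency as the mean count per available evening entry plus the mean count per available morning entry in the window, or use only diary days with both entries.
- State a minimum number of each below which the visit value is missing.
- Apply the rule identically at baseline, at every visit, at any interim still to come, and to the hot flush score.
- Keep the current rule as a sensitivity analysis, and report one-entry days by arm and visit.
- State how the vendor's eligibility mean treats one-entry days.
- Settle the SAP 4.2.11 conflict between assuming no flushes and not using the diary.

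**Cost.** This is SAP wording and a small derivation change; Protocol 11.12 already leaves missing-value rules to the SAP. SAP 3.1 describes the blinded review as finished, and interims already held cannot be redone. A few visit values become missing. As an example, take a minimum of 4 evening and 4 morning entries in the 14-day window. Almost none are lost at 10% missing entries. For a subject missing half, P(Bin(14, 0.5) ≤ 3) = 0.0287, so 1 - (1 - 0.0287)² = 5.7%. The simulation shows no loss of precision, though its gaps were unrelated to symptoms. Both alternatives rely on missing entries resembling the subject's recorded ones, and the SAP should say so.
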